#### **7.2.3.2 Events of Clinical Interest**

Selected non-serious and serious adverse events are also known as Events of Clinical Interest (ECI) and must be reported to the Sponsor.

For the time period beginning when the consent form is signed until treatment allocation/randomization, any ECI, or follow up to an ECI, that occurs to any subject must be reported within 24 hours to the Sponsor if it causes the subject to be excluded from the trial, or is the result of a protocol-specified intervention, including but not limited to washout or discontinuation of usual therapy, diet, placebo treatment or a procedure.

For the time period beginning at treatment allocation/randomization through 30 days following cessation of treatment, any ECI, or follow up to an ECI, whether or not related to the Sponsor's product, must be reported within 24 hours to the Sponsor, either by electronic media or paper. Electronic reporting procedures can be found in the EDC data entry guidelines. Paper reporting procedures can be found in the Investigator Trial File Binder (or equivalent).

Events of clinical interest for this trial include:

1. an overdose of Sponsor's product, as defined in Section 7.2.1 - Definition of an Overdose for This Protocol and Reporting of Overdose to the Sponsor, that is not associated with clinical symptoms or abnormal laboratory results.

2. an elevated AST or ALT lab value that is greater than or equal to 3X the upper limit of normal and an elevated total bilirubin lab value that is greater than or equal to 2X the upper limit of normal and, at the same time, an alkaline phosphatase lab value that is less than 2X the upper limit of normal, as determined by way of protocol-specified laboratory testing or unscheduled laboratory testing.\*

\*Note: These criteria are based upon available regulatory guidance documents. The purpose of the criteria is to specify a threshold of abnormal hepatic tests that may require an additional evaluation for an underlying etiology. The trial site guidance for assessment and follow up of these criteria can be found in the Investigator Trial File Binder (or equivalent).

#### **7.2.3.3 Protocol-Specific Exceptions to Serious Adverse Event Reporting**

Immediate Reporting of AEs to the Sponsor must be done. Any such event will be submitted to the Sponsor within 24 hours either by electronic or paper media.

Specifically, the suspected/actual events covered in this exception include any event that is disease progression of the cancer under study.

The Sponsor will monitor unblinded aggregated safety data to ensure the safety of the subjects in the trial. Any suspected endpoint which upon review is not progression of the cancer under study will be forwarded to global safety as a serious adverse event within 24 hours of determination that the event is not progression of the cancer under study

#### **7.2.4 Evaluating Adverse Events**

An investigator who is a qualified physician will evaluate all adverse events according to the NCI Common Terminology for Adverse Events (CTCAE), version 4.0. Any adverse event which changes CTCAE grade over the course of a given episode will have each change of grade recorded on the adverse event case report forms/worksheets.

All adverse events regardless of CTCAE grade must also be evaluated for seriousness.

Table 7 Evaluating Adverse Events

An investigator who is a qualified physician, will evaluate all adverse events as to:

V4.0 CTCAE Grading	Grade 1	Mild; asymptomatic or mild symptoms; clinical or diagnostic observations only; intervention not indicated.
	Grade 2	Moderate; minimal, local or noninvasive intervention indicated; limiting age-appropriate instrumental ADL.
	Grade 3	Severe or medically significant but not immediately life-threatening; hospitalization or prolongation of hospitalization indicated; disabling; limiting self-care ADL.
	Grade 4	Life threatening consequences; urgent intervention indicated.
	Grade 5	Death related to AE
Seriousness	A serious adverse event is any adverse event occurring at any dose or during any use of Sponsor's product that:	
	† Results in death ; or	
	† Is life threatening ; or places the subject, in the view of the investigator, at immediate risk of death from the event as it occurred (Note: This does not include an adverse event that, had it occurred in a more severe form, might have caused death.); or	
	† Results in a persistent or significant disability/incapacity (substantial disruption of one's ability to conduct normal life functions); or	
	† Results in or prolongs an existing inpatient hospitalization (hospitalization is defined as an inpatient admission, regardless of length of stay, even if the hospitalization is a precautionary measure for continued observation. (Note: Hospitalization for an elective procedure to treat a pre-existing condition that has not worsened is not a serious adverse event. A pre-existing condition is a clinical condition that is diagnosed prior to the use of an MSD product and is documented in the patient's medical history.); or	
	† Is a congenital anomaly/birth defect (in offspring of subject taking the product regardless of time to diagnosis); or	
	Is a new cancer (that is not a condition of the study) (although not serious per ICH definition, is reportable to the Sponsor within 24 hours to meet certain local requirements); or	
	Is an overdose (whether accidental or intentional). Any adverse event associated with an overdose is considered a serious adverse event for collection purposes. An overdose that is not associated with an adverse event is considered a non-serious event of clinical interest and must be reported within 24 hours.	
	Other important medical events that may not result in death, not be life threatening, or not require hospitalization may be considered a serious adverse event when, based upon appropriate medical judgment, the event may jeopardize the subject and may require medical or surgical intervention to prevent one of the outcomes listed previously (designated above by a †).	
Duration	Record the start and stop dates of the adverse event. If less than 1 day, indicate the appropriate length of time and units	
Action taken	Did the adverse event cause the Sponsor's product to be discontinued?	
Relationship to Sponsor's Product	Did the Sponsor's product cause the adverse event? The determination of the likelihood that the Sponsor's product caused the adverse event will be provided by an investigator who is a qualified physician. The investigator's signed/dated initials on the source document or worksheet that supports the causality noted on the AE form, ensures that a medically qualified assessment of causality was done. This initialed document must be retained for the required regulatory time frame. The criteria below are intended as reference guidelines to assist the investigator in assessing the likelihood of a relationship between the test drug and the adverse event based upon the available information.  The following components are to be used to assess the relationship between the Sponsor's product and the AE ; the greater the correlation with the components and their respective elements (in number and/or intensity), the more likely the Sponsor's product caused the adverse event (AE):	
	Exposure	Is there evidence that the subject was actually exposed to the Sponsor's product such as: reliable history, acceptable compliance assessment (pill count, diary, etc.), expected pharmacologic effect, or measurement of drug/metabolite in bodily specimen?
	Time Course	Did the AE follow in a reasonable temporal sequence from administration of the Sponsor's product? Is the time of onset of the AE compatible with a drug-induced effect (applies to trials with investigational medicinal product)?
	Likely Cause	Is the AE not reasonably explained by another etiology such as underlying disease, other drug(s)/vaccine(s), or other host or environmental factors

Relationship to Sponsor's Product (continued)	The following components are to be used to assess the relationship between the test drug and the AE: (continued)	
	Dechallenge	Was the Sponsor's product discontinued or dose/exposure/frequency reduced? If yes, did the AE resolve or improve? If yes, this is a positive dechallenge. If no, this is a negative dechallenge. (Note: This criterion is not applicable if: (1) the AE resulted in death or permanent disability; (2) the AE resolved/improved despite continuation of the Sponsor's product; or (3) the trial is a single-dose drug trial); or (4) Sponsor's product(s) is/are only used one time.)
	Rechallenge	Was the subject re-exposed to the Sponsor's product in this study? If yes, did the AE recur or worsen? If yes, this is a positive rechallenge. If no, this is a negative rechallenge. (Note: This criterion is not applicable if: (1) the initial AE resulted in death or permanent disability, or (2) the trial is a single-dose drug trial); or (3) Sponsor's product(s) is/are used only one time). NOTE: IF A RECHALLENGE IS PLANNED FOR AN ADVERSE EVENT WHICH WAS SERIOUS AND WHICH MAY HAVE BEEN CAUSED BY THE SPONSOR'S PRODUCT, OR IF REEXPOSURE TO THE SPONSOR'S PRODUCT POSES ADDITIONAL POTENTIAL SIGNIFICANT RISK TO THE SUBJECT, THEN THE RECHALLENGE MUST BE APPROVED IN ADVANCE BY THE SPONSOR CLINICAL DIRECTOR AS PER DOSE MODIFICATION GUIDELINES IN THE PROTOCOL.
Consistency with Trial Treatment Profile	Is the clinical/pathological presentation of the AE consistent with previous knowledge regarding the Sponsor's product or drug class pharmacology or toxicology?	
The assessment of relationship will be reported on the case report forms /worksheets by an investigator who is a qualified physician according to his/her best clinical judgment, including consideration of the above elements.		
Record one of the following	Use the following scale of criteria as guidance (not all criteria must be present to be indicative of a Sponsor's product relationship).	
Yes, there is a reasonable possibility of Sponsor's product relationship.	There is evidence of exposure to the Sponsor's product. The temporal sequence of the AE onset relative to the administration of the Sponsor's product is reasonable. The AE is more likely explained by the Sponsor's product than by another cause.	
No, there is not a reasonable possibility of Sponsor's product relationship	Subject did not receive the Sponsor's product OR temporal sequence of the AE onset relative to administration of the Sponsor's product is not reasonable OR the AE is more likely explained by another cause than the Sponsor's product. (Also entered for a subject with overdose without an associated AE.)	

## 7.2.5 Sponsor Responsibility for Reporting Adverse Events

All Adverse Events will be reported to regulatory authorities, IRB/IECs and investigators in accordance with all applicable global laws and regulations, i.e., per ICH Topic E6 (R1) Guidelines for Good Clinical Practice.

## 8.0 STATISTICAL ANALYSIS PLAN

This section outlines the statistical analysis strategy and procedures for the study. If, after the study has begun, but prior to any final database lock, changes are made to the primary and/or key secondary hypotheses, or the statistical methods related to those hypotheses, then the protocol will be amended (consistent with ICH Guideline E-9). Changes to exploratory or other non-confirmatory analyses made after the protocol has been finalized, but prior to final database lock, will be documented in a supplemental SAP (sSAP) and referenced in the Clinical Study Report (CSR) for the study. Post hoc exploratory analyses will be clearly identified in the CSR.

### 8.1 Statistical Analysis Plan Summary

Key elements of the statistical analysis plan are summarized below; the comprehensive plan is provided in Sections 8.2-8.12.

Study Design Overview	A Prospective, Open-label, Phase 4 Study to Evaluate the Safety of Pembrolizumab (Keytruda®) in Subjects with Unresectable or Metastatic Melanoma or PD-L1 positive Non-Small Cell Lung Cancer (NSCLC) in India
Treatment Assignment	All subjects to be assigned to the same dose/schedule of pembrolizumab
Analysis Populations	ASaT
Primary Endpoint(s)	Safety and tolerability of the protocol treatment as characterized by the adverse event experience
Statistical Methods for Key Safety Analyses	Descriptive statistics will be provided for the rate of safety endpoints.
Interim Analyses	An ongoing safety review will be conducted for this study. An interim data listing for safety evaluation will be conducted at 1 year from the date at which the first subject is enrolled into the study.
Multiplicity	Not applicable
Sample Size and Power	The planned sample size is approximately 150 subjects (with a minimum of 25 subjects with unresectable or metastatic melanoma, and ~125 NSCLC subjects who are either untreated (PD-L1 $\geq$ 50%) or have experienced disease progression after a platinum-containing systemic therapy (PD-L1 $\geq$ 1%). No hypothesis testing will be performed. The goal is to characterize the AEs associated with the use of pembrolizumab in the treatment of subjects, as described above, in India.

## 8.2 Responsibility for Analyses/In-House Blinding

The statistical analysis of the data obtained from this study will be the responsibility of the Clinical Biostatistics department of the Sponsor.

This trial is being conducted as a non-randomized, open-label study, i.e., subjects, investigators, and Sponsor personnel will be aware of subject treatment assignments after each subject is enrolled and treatment is assigned.

## 8.3 Hypotheses/Estimation

Objectives and hypotheses of the study are stated in Section 3.0

## 8.4 Analysis Endpoints

The safety endpoints that will be evaluated are listed below.

### 8.4.1 Safety Endpoints

See Section 4.2.3.2 for the initial description of safety measures.

## 8.5 Analysis Populations

### 8.5.1 Safety Analysis Populations

The All Subjects as Treated (ASaT) population will be used for the analysis of safety data in this study. The ASaT population consists of all subjects who received at least 1 dose of trial treatment.

At least 1 laboratory or vital sign measurement obtained subsequent to at least 1 dose of trial treatment is required for inclusion in the analysis of each specific parameter. To assess change from baseline, a baseline measurement is also required.

## 8.6 Statistical Methods

### 8.6.1 Statistical Methods for Safety Analyses

Safety and tolerability will be assessed by clinical review of all relevant parameters including AEs and laboratory parameters.

The proportion of subjects with AEs of elevated laboratory values that are reported as ECIs described in Section 7.2.3.2 during the study therapy period will be provided along with the corresponding 95% CIs, which will be calculated using the Clopper Pearson method.

In addition, the broad AE categories consisting of the percentage of subjects with any AE, a drug-related AE, a serious AE, an AE which is both drug-related and serious, and those who discontinued due to an AE will be summarized in the same manner [Table 8](#).

Table 8 Analysis Strategy for Safety Parameters

Safety Endpoint	Within Group 95% CI	Descriptive Statistics
Any AE	X	X
Any Serious AE	X	X
Any Drug-Related AE	X	X
Any Serious and Drug-Related AE	X	X
Discontinuation due to AE	X	X
Specific AEs, SOCs, or PDLCs ‡ (incidence $\geq 1\%$ of participants)	X	X
Specific AEs, SOCs or PDLCs ‡ (incidence <1% of participants)		X
Change from Baseline Results (Labs, ECGs, Vital Signs)		X
Note: SOC=System Organ Class; X = results will be provided. 95% CIs will be calculated using the Clopper Pearson method.		

For continuous measures such as changes from baseline in laboratory, vital signs, and ECG parameters, summary statistics for baseline, on-treatment, and change from baseline values may be provided in table format. Mean change from baseline over time may also be plotted with the corresponding standard errors.

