
1. Documented informed consent and audiovisual recording of the documented informed consent process must be obtained prior to performing any protocol-specific procedure. Results of a test performed as part of routine clinical management are acceptable in lieu of a screening test if performed within 30 days prior to Cycle 1, Day 1). Assign Baseline number when the study informed consent is documented.
 
2. Includes history of treatment for the primary diagnosis, including prior systemic, radiation treatment and surgical treatment, and best response to prior systemic treatments within the previous 10 years. Date of last prior cancer treatment must be documented. Radiographic studies performed prior to study entry may be collected for review by the investigator. Report complete medication history taken within 30 days prior to the screening visit (Visit 1).
 
3. All AEs should be reported for at least 30 days following treatment cessation. Serious adverse events and ECIs should be reported for 90 days following treatment cessation. A serious adverse event considered drug-related by the investigator should be reported regardless of how long has elapsed since treatment cessation. Pregnancies and lactation events should be reported for 120 days following treatment cessation or for 30 days if the subject initiates new anticancer therapy.
 
4. ECOG of 0 or 1 is required at screening and at C1D1.
 
5. Vital signs to include temperature, pulse, respiratory rate, and blood pressure. If a subject's baseline weight does not fluctuate by more than 10%, this weight can be used to calculate dose. Height will be measured at screening only.
 
6. A 12-lead ECG will be performed at Screening and at every fourth cycle starting on Cycle 4.
 
7. Routine laboratory tests (serum or plasma chemistry and hematology) for screening must be performed within 10 days prior to administration of the first dose. If a subject starts screening > 10 days prior to administration of trial treatment, a second screening visit is required to collect the lab specimens within the specified timeframe.
 
8. Testing will be performed by the local laboratory at Screening: Hepatitis B and C serologies should be obtained for subjects without a known history of hepatitis B or C. Those with a known history are ineligible. Include HCV RNA (qualitative) and HbsAg.
 
9. For females of reproductive potential, urine or serum pregnancy test should be performed within 72 hours prior to day 1 of each treatment cycle and 30 days post treatment if required or as specified per local regulatory guidance. A serum test can be done if urine is not appropriate. Additionally, if urine test is positive or is not evaluable, a serum test is required. Subjects must be excluded/discontinued in the event of a positive test result.
 
10. PT/INR and aPTT should be collected at Screening and at the Safety Follow-up Visit after discontinuation of study therapy. Coagulation parameters will be determined throughout the study if clinically indicated. PT/INR and aPTT will be analyzed by the local study site laboratory.
 
11. Routine laboratory tests (e.g., CBC with differential, comprehensive serum or plasma chemistry panel, and urinalysis) will be performed by the local study site laboratory or their contract laboratory. Additionally, CBC with differential and comprehensive serum or plasma chemistry panel are to be collected up to 48 hours prior to Day 1 dosing of any Cycle.
 
12. Following baseline and Cycle 2, urinalysis should be performed every fourth cycle.
 
13. Analysis of T3, FT4, and TSH will be performed by the local study site laboratory or their contract laboratory. Following Cycle 2, testing will be performed every other cycle.
													

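### Section 8.6.1 counts the hepatic laboratory ECI from site reports only, although Section 7.2.3.2 defines it by numeric thresholds on routinely collected values, and Section 8 has no check for unreported cases

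*Combined protocol and SAP*

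**What the plan says.** **How the event is counted.** Section 8.6.1 estimates a subject-level proportion for "AEs of elevated laboratory values that are reported as ECIs described in Section 7.2.3.2", limited to the study therapy period, with "corresponding 95% CIs, which will be calculated using the Clopper Pearson method".

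**How the event is defined.** Section 7.2.3.2 lists two ECIs. One is an overdose without symptoms or abnormal laboratory results. The other, the only laboratory ECI, has three numeric parts:
- "an elevated AST or ALT lab value that is greater than or equal to 3X the upper limit of normal";
- "an elevated total bilirubin lab value that is greater than or equal to 2X the upper limit of normal";
- "at the same time, an alkaline phosphatase lab value that is less than 2X the upper limit of normal".

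The values count "as determined by way of protocol-specified laboratory testing or unscheduled laboratory testing".

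**Where the values come from.** Table 6 lists ALT, AST, total bilirubin and ALP in the chemistry panel. The flow chart (Section 6.0) schedules that panel at screening, at every cycle from Cycle 2 and at safety follow-up. Footnote 11 adds, with reference to the treatment cycles: "CBC with differential and comprehensive serum or plasma chemistry panel are to be collected up to 48 hours prior to Day 1 dosing of any". The site's own or contract laboratory performs the tests.

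**How the event is reported.** For the period from allocation to 30 days after treatment ends, Section 7.2.3.2 sets this duty: "any ECI, or follow up to an ECI, whether or not related to the Sponsor's product, must be reported within 24 hours to the Sponsor".

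**The concern.** The protocol defines the event by laboratory values, but the analysis counts it by site reports. To file the ECI, a site must compare several local results with its local upper limits of normal (ULN), recognise that the three parts coincide, and report within 24 hours. If it does not, the subject stays in the denominator and drops out of the numerator.

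Section 8 contains nothing that would reveal this. It neither derives the criterion from the values nor reconciles reports with them. The change-from-baseline summaries in Section 8.6.1 are optional, carry no CI, and describe continuous parameters; they cannot show a three-part coincidence in one subject.

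Safety is the trial's only objective, and Section 8.7.1 sends the safety review results to the regulator for direction on continuing. With few expected cases, one or two omissions would change the point estimate noticeably.

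**Working it through.** **1. Reproduce the plan's own intervals.** Section 8.9.1 tabulates 95% CIs for n = 150. The Clopper-Pearson limits for x events are

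- lower = 2.5% quantile of Beta(x, n − x + 1)
- upper = 97.5% quantile of Beta(x + 1, n − x)

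For x = 8 these give 2.33% and 10.24%, printed as (2.3%, 10.2%). For x = 53 they give 27.71% and 43.55%, printed as (27.7%, 43.5%). All seven rows agree with the printed table.

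**2. Illustrate an omission.** The documents give no expected count for this ECI, so the counts below are assumptions.

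| Meet the threshold | Reported as ECI | Derived proportion (95% CI) | Planned proportion (95% CI) |
|---|---|---|---|
| 3 | 2 | 2.00% (0.41, 5.73) | 1.33% (0.16, 4.73) |
| 4 | 2 | 2.67% (0.73, 6.69) | 1.33% (0.16, 4.73) |
| 6 | 3 | 4.00% (1.48, 8.50) | 2.00% (0.41, 5.73) |

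**3. Vary the rate and the completeness of reporting.** Let p be the true rate and s the fraction of true cases reported, with no false reports. The reported count is then Binomial(150, p × s), the expected reported rate is p × s, and the chance of no reported case is (1 − p × s)^150. Coverage is the probability that the planned interval contains p. Both p and s are assumed.

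| p | s | Expected reported rate | Chance of no reported case | Coverage of p |
|---|---|---|---|---|
| 1% | 100% | 1.00% | 22.1% | 98.2% |
| 1% | 50% | 0.50% | 47.1% | 99.9% |
| 2% | 100% | 2.00% | 4.8% | 98.9% |
| 2% | 75% | 1.50% | 10.4% | 99.8% |
| 2% | 50% | 1.00% | 22.1% | 100.0% |
| 4% | 100% | 4.00% | 0.2% | 96.6% |
| 4% | 90% | 3.60% | 0.4% | 96.5% |
| 4% | 75% | 3.00% | 1.0% | 94.0% |
| 4% | 50% | 2.00% | 4.8% | 80.4% |

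At 1% to 2% the exact interval is wide enough to absorb the omissions, so the harm is to the point estimate and to the chance of seeing any case. Coverage fails clearly only at 4% with half the cases missed.

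**4. Check whether a raw threshold count would be clean.** Table 2 admits AST/ALT up to 5 × ULN with liver metastases, and total bilirubin above 1.5 × ULN if direct bilirubin is within normal limits. It sets no ALP limit. A subject could therefore enter with AST at 3 to 5 × ULN, total bilirubin at 2 × ULN or more and ALP below 2 × ULN, and meet the criterion before the first dose. A derived count needs a baseline rule.

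**5. Check the window.** Section 8 does not define the study therapy period. Section 7.2.3.2 sets the ECI reporting period at 30 days after treatment; flow chart footnote 3 says 90 days. These passages must be reconciled before either count is fixed.

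**The case against.** The strongest reply is that the protocol already works against omissions. Subjects are assessed for possible ECIs before each dose (Section 7.1.2.1). Laboratory results must be reviewed and found acceptable before each dose (Section 7.1.3.1). ECIs must be reported whether or not they are related to treatment. The sponsor reviews data for completeness and verifies them against source (Section 12.1). Data-management procedures are provided separately (Section 10.6), so some reconciliation may happen outside the SAP. All of this stands, and it limits the likely miss rate. It does not supply a check within the analysis.

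A reader might go further and infer that an unreported case is a liver signal that nobody followed up. The documents do not support that. Besides the reviews above, Table 4 sets out actions and liver-test monitoring for immune-related AST, ALT or bilirubin elevation from Grade 2, and Section 8.6.1 includes clinical review of laboratory parameters. A case not filed as an ECI is not thereby unreviewed.

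A reader might also infer that this is the only laboratory endpoint with a CI. It is the only one singled out in the text of Section 8.6.1, but Table 8 also gives CIs to specific AEs, which can include laboratory findings, and to PDLCs, at incidence of 1% or more. PDLC is not explained in the text available, so whether that row holds a derived liver threshold cannot be told. It would in any case give no CI to a single case, since 1/150 = 0.67%.

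Finally, this is a single-arm descriptive study, and AE rates generally rest on investigator reports. That convention suits events that need clinical judgement. It is a weaker defence for an event defined wholly by numbers that the trial schedules for collection.

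**Conclusion.** The point holds as a gap in the analysis plan. The laboratory ECI proportion rests on reports alone, the criterion can be computed from scheduled tests, and Section 8 would not show a discrepancy.

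The size is not known from the documents. Halving 2.7% to 1.3% assumes 4 qualifying subjects among 150 and 2 missed reports; even then the planned interval of 0.2% to 4.7% contains 2.7%.

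It might be inferred that the planned rate will be too low. Omissions alone can only lower it, but ECIs filed in error would raise it, and the documents establish neither frequency. Nor do they support simply replacing the reported count with a raw threshold count, because some subjects may meet the threshold at entry. The two counts belong side by side. The change is inexpensive and should be made, although it does not undermine the trial's objective.

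**What to change.** In Section 8.6.1, keep the reported-ECI proportion and add a laboratory-derived one:

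1. Apply the Section 7.2.3.2 criterion to all scheduled and unscheduled AST, ALT, total bilirubin and ALP values after the first dose, each against the local ULN.
2. State the time window within which the values count as simultaneous.
3. State how subjects who already meet or nearly meet the threshold at baseline are handled.
4. Define one analysis window for both counts, after reconciling the 30-day period in Section 7.2.3.2 with the 90-day period in flow chart footnote 3.
5. Report the derived proportion with its Clopper-Pearson 95% CI beside the reported-ECI proportion and CI.
6. List discordant subjects, in both directions, for medical review. Do this at the 1-year interim listing (Section 8.7.1) as well as at the end.

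The cost is one derived variable, one listing, and local reference ranges in the database. The documents do not say how those ranges are captured, so this needs confirming. The rate presented may change slightly.

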##### **4.2.3.2 Safety Endpoints**

Safety parameters commonly used for evaluating investigational systemic anti-cancer treatments are included as safety endpoints for the study including, but not limited to, the incidence of, causality, severity, and outcome of adverse events/serious adverse events; changes in vital signs and laboratory values. Adverse events will be assessed as defined by Common Terminology for Adverse Events (CTCAE), Version 4.0.

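### Outside one hepatic event of clinical interest and investigator-reported AEs, laboratory values get only optional summary statistics and mean change; a baseline-to-worst-grade shift table should be added and PDLC defined or deleted

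*Combined protocol and SAP*

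**What the plan says.** Section 4.2.3.2 lists the safety endpoints as including "the incidence of, causality, severity, and outcome of adverse events/serious adverse events; changes in vital signs and laboratory values". Severity is attached to adverse events; laboratory data enter as changes.

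Section 8.6.1 and Table 8 then give laboratory data four possible outlets:

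- **Continuous summaries.** For laboratory, vital-sign and ECG measures, "summary statistics for baseline, on-treatment, and change from baseline values may be provided in table format". The next sentence adds that "Mean change from baseline over time may also be plotted with the corresponding standard errors". Both are permissive. The Table 8 row for change from baseline is marked for descriptive statistics only, with no confidence interval.
- **Laboratory ECI.** A proportion with a Clopper-Pearson 95% CI is promised for "The proportion of subjects with AEs of elevated laboratory values that are reported as ECIs described in Section 7.2.3.2 during the study therapy period". Section 7.2.3.2 defines one laboratory ECI: "an elevated AST or ALT lab value that is greater than or equal to 3X the upper limit of normal", together with total bilirubin at or above 2x ULN and, at the same time, alkaline phosphatase below 2x ULN.
- **AE incidence.** Abnormal laboratory findings can be AEs under Section 7.2, and then count in the AE rows of Table 8.
- **PDLCs.** Table 8 has incidence rows for "Specific AEs, SOCs, or PDLCs", with a CI at 1% incidence or more. The footnote mark has no text, Section 12.6 does not expand the abbreviation, and no limits appear anywhere.

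Section 8 contains no shift table, worst on-treatment value or worst grade for laboratory data.

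**The concern.** Laboratory toxicity of clinical importance is often a large change in a few subjects. A mean over the whole group spreads that change across everyone. A mean by visit also loses the most affected subjects over time: Table 4 calls for permanent discontinuation at Grade 3 or 4 for hepatic and renal immune-related events, so means at later cycles describe those who remained on treatment.

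The other outlets leave gaps. An isolated large ALT rise without the bilirubin criterion is not an ECI, nor is any creatinine, glucose, thyroid or hematology abnormality. The AE route depends on a judgement that the protocol does not standardise for laboratory results. Sections 7.1.2.3 and 7.1.2.5 say when physical-examination and ECG findings must be recorded as AEs; Section 7.1.3.1 has no matching rule. Table 8 has no grade category either, although Section 8.9.1 speaks of Grade 3+ events.

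At stake is whether the report can state, from the measured values, how many subjects went from an acceptable baseline to a severe abnormality on each test. Baseline matters here because Table 2 admits subjects with liver metastases at AST/ALT up to 5x ULN, so a post-baseline abnormality alone is ambiguous.

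**Working it through.** **Inputs from the documents.** Planned N = 150 and the interval table (Section 8.9.1); Clopper-Pearson 95% intervals (Section 8.6.1); CBC and chemistry at screening, at each cycle from Cycle 2 and at safety follow-up (Section 6.0).

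**Assumed inputs.** The documents give no laboratory SD and no rate of laboratory toxicity. I assume that k subjects rise from 1x to m times ULN at the same visit, and that the others average no change with SD 0.3x ULN. I also assume that the raised values fall in Grade 3-4; the protocol cites CTCAE v4.0 but does not reproduce its cut points.

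**1. The plan's own figures.** The exact limits for x of n are the beta quantiles B(0.025; x, n-x+1) and B(0.975; x+1, n-x). With n = 150:

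| x | Recomputed 95% CI | Section 8.9.1 |
|---|---|---|
| 8 | 2.33% to 10.24% | 2.3% to 10.2% |
| 15 | 5.71% to 15.96% | 5.7% to 16.0% |
| 23 | 9.98% to 22.11% | 10.0% to 22.1% |
| 30 | 13.92% to 27.30% | 13.9% to 27.3% |
| 38 | 18.59% to 33.07% | 18.6% to 33.1% |
| 45 | 22.80% to 38.01% | 22.8% to 38.0% |
| 53 | 27.71% to 43.55% | 27.7% to 43.5% |

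All seven rows agree (the last upper limit is 43.548% before rounding). The plan states no figure for the laboratory summaries.

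**2. Effect on the mean.** Mean change = k(m - 1)/150.

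- k = 3, m = 10: 3 x 9/150 = 0.18x ULN. The variance before the n-1 correction is (147 x 0.3² + 3 x 9²)/150 - 0.18² = 1.708 - 0.032 = 1.676, so SD = √(1.676 x 150/149) = 1.30 and SE = 1.30/√150 = 0.11. The mean is 1.7 SE from zero.
- If the three peaks fall at different visits, each visit's mean moves by 1 x 9/150 = 0.06x ULN.
- k = 5, m = 10: 5 x 9/150 = 0.30x ULN, SE 0.135, which is 2.2 SE from zero.
- Range over k = 1 to 5 and m = 3 to 20: from 1 x 2/150 = 0.01 to 5 x 19/150 = 0.63x ULN.

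These use the full 150. With fewer subjects at a later visit, one remaining outlier moves the mean more, but those who have stopped contribute nothing to it.

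**3. The same subjects in a worst-grade table.**

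| Subjects in the severe cells | Proportion | Exact 95% CI |
|---|---|---|
| 1/150 | 0.7% | 0.02% to 3.7% |
| 3/150 | 2.0% | 0.4% to 5.7% |
| 5/150 | 3.3% | 1.1% to 7.6% |

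This count does not depend on whether the peaks coincide or on who is still treated at later cycles.

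**4. Would there be anything to show?** The chance of at least one case is 1 - (1 - p)^150. At a true rate of 1% this is 1 - 0.99^150 = 78%; at 2% it is 1 - 0.98^150 = 95%.

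**The case against.** A reader might infer that laboratory safety is summarised by mean change alone, and that the report would look flat while several subjects had Grade 3-4 changes. The documents do not support that reading, for four reasons.

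- The quoted plot is optional and is not the stated laboratory analysis. The summary statistics are not listed, so they could include a range or maximum. The ECI proportion with an exact interval is a firm commitment.
- The AE route has real structure. Section 7.1.3.1 requires results to be reviewed and found acceptable before each dose. Table 4 names graded hepatic, renal, glycemic and thyroid events. Section 7.2.4 grades AEs by CTCAE v4.0 and records each change of grade. Such events then appear in Table 8 as specific AEs, drug-related AEs or discontinuations due to an AE.
- A mean need not look flat. Five subjects at 10x ULN put it 2.2 SE above zero in the calculation above.
- The trial tests no hypothesis, so another display changes no decision rule.

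All four points stand, and they limit the concern. They do not remove it. A mean away from zero does not say how many subjects were affected or how severely. A maximum shows one subject, not a count by grade. The AE rows count what was reported as an AE and, as laid out, do not separate grades. The ECI covers one hepatic pattern. The PDLC row cannot be programmed without limits.

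**Conclusion.** The concern holds in a limited form. Outside the hepatic ECI and reported AEs, laboratory values have only optional summary statistics and mean change. Neither gives the number of subjects with a severe worst value by test, and PDLC is undefined. A worst-grade shift table would be a clearly better summary for a trial whose only aim is safety.

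The size is illustrative. Three severe cases give a mean shift of 0.18x ULN (0.06x per visit if the peaks do not coincide), against a visible 2.0% (95% CI 0.4% to 5.7%). The mean shift rests on the assumed counts, peak, SD and N = 150; the percentage rests on the count, N = 150 and the assumption that these values grade as 3-4. The gap in the plan does not rest on any of these.

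The effect is on reporting only. Sample size and the planned AE analyses are unchanged. Nothing in the documents shows that severe cases would go unrecorded; the shift table would be a check on AE reporting that uses the measured values.

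**What to change.** In Section 8.6.1 and Table 8:

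1. Add, for each Table 6 test that CTCAE v4.0 grades numerically, a table of baseline grade against worst post-baseline grade. Use low/normal/high categories where no numeric grade exists.
2. Use all available scheduled and unscheduled values through 30 days after the last dose. The word available matters, because Section 7.1.3.1 waives repeat tests after the end of treatment when results are normal.
3. Give n (%) with Clopper-Pearson 95% CI for shifts to Grade 3-4.
4. Define PDLC, with limits by test and the missing footnote text, or delete it.
5. Keep mean change as supportive, next to the ECI and AE summaries.

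**Cost.** No new visit, sample or subject. Baseline and post-dose values are already required by Section 8.5.1 for change from baseline, and the interval method is already in the plan. The real work is programming. CTCAE v4.0 is specified for AEs, so grading of numeric results must be added. Routine tests use local or contract laboratories, and Section 10.3 mentions reference ranges only as retained documentation, so each laboratory's limits must be brought into the database. As a non-confirmatory change, it could be documented in the supplemental SAP that Section 8.0 allows before final database lock.
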